## 1. Introduction

This Statistical Analysis Plan (SAP) is based on study procedures and analyses described in the protocol Number: M200C-2102 dated August 25, 2021. Table/Figure shells and mock listings corresponding to the contents of this document will be in a separate file.

### 1.1 Background

IXT-m200, also called ch-mAb7F9, binds METH with high selectivity and affinity. The product contains a murine METH-binding variable region and the constant domains of a human immunoglobulin G (IgG) 2κ. This antibody isotype was chosen because of the lower risk of immune response compared to an IgG1 or IgG3. IXT-m200 targets METH, does not rely on binding to any endogenous target for its action, and has been well-tolerated in previous clinical studies (see below).

Through the binding of METH in the bloodstream, it is anticipated that IXT-m200 will alter the pharmacokinetics (PK) of METH and decrease concentrations of METH reaching its active sites in the brain. The presence of IXT-m200 should therefore decrease the perceived pleasurable effects of METH. Over the longer term, when combined with behavioral therapy, IXT-m200 should reduce the frequency of METH use over time.

### 1.2 IXT-m200 Pharmacokinetics in Healthy Volunteers

A Phase 1 study of the safety of single doses of IXT-m200 in healthy humans has been completed. In this first clinical study, 42 participants (17 females) were dosed in 5 groups (0.2, 0.6, 2, 6, or 20 mg/kg IXT-m200), with 10 participants receiving placebo (saline). Pharmacokinetic results indicated that IXT-m200 is similar to other IgGs, with an elimination half-life of ~18 days, volume of distribution (Vd) of ~5 L and clearance of ~200 mL/d. The disposition of IXT-m200 did not appear to be affected by dose.

### 1.3 IXT-m200 Safety and Tolerability

There were no serious adverse events (SAEs) or serious adverse reactions during the conduct of the Phase 1 study. There were 3 adverse events in 2 participants that were attributed to IXT-m200. A mild infusion reaction (Common Terminology Criteria for Adverse Events (CTCAE) v.4.0 Grade 3) and bronchospasm (Grade 2) occurred in the same participant. The symptoms included a brief period of bronchospasm with no drop in oxygen saturation that resolved with stopping the infusion. A separate participant experienced an AE of mild proteinuria (Grade 1). Both participants were in the same dose group (2 mg/kg IXT-m200).

Samples from all participants were tested for immunogenicity, i.e., anti-IXT-m200 antibodies. Samples from only 4 (12.5%) IXT-m200 treated participants were confirmed to have low titers. One of these 4 participants also provided a pre-dose sample that screened positive for

---

anti-IXT-m200 antibodies. The development of anti-IXT-m200 antibodies did not appear to be dose-related. Overall, there were no apparent safety or tolerability concerns identified when IXT-m200 was dosed over the range from 0.2 to 20 mg/kg. Therefore, a maximum tolerated dose was not reached.

Following the Phase 1 study, a Phase 2 study of IXT-m200 was conducted (STAMPOUT: Study of Antibody for Methamphetamine Outpatient Therapy, NCT03336866). This was a parallel-group, placebo-controlled, double-blind study in otherwise healthy, non-treatment seeking participants who use METH. Those who qualified received single doses of IXT-m200 (6 or 20 mg/kg) or placebo followed by weekly METH challenges for up to 4 weeks. The challenges consisted of METH (30 mg, intravenous) and placebo, separated by 4 hours. Safety, METH and IXT-m200 PK, and pharmacodynamic data were collected for up to 126 days.

In the STAMPOUT study, all AEs were grade 1 or grade 2. Common AEs included palpitations, tachycardia, dry mouth, nausea, injection site pain, headache, euphoria, hypervigilance, and hyperhidrosis. All of these AEs are expected in people receiving METH, and all participants in this study received METH. Of these, only blurred vision, nausea, feeling abnormal, and dry mouth were considered by the investigator as probably related to IXT-m200; each AE was reported by only one participant who received IXT-m200. Furthermore, none of the AEs associated with METH appeared to be exacerbated by IXT-m200. For example, an analysis of heart rate changes following METH administration demonstrated that average percent heart rate increase, and average peak heart rates were not changed in the presence of IXT-m200. Plus, the individual maximum attained heart rate in each group was 139 (placebo), 142 (6 mg/kg), and 144 (20 mg/kg). Finally, as in the Phase 1 study, samples from all participants were tested for HACA. Only one participant in each IXT-m200 dose group had notable titers of anti-IXT-m200 antibodies, and the PK of IXT-m200 in these participants did not differ from other participants in the dose group.

## 1.4 Justification for IXT-m200 Dose

The IXT-m200 dose of 3 g was selected for this study because it is potentially effective in reducing METH effects for several weeks, and will be used in an upcoming repeat-dose Phase 2 clinical study in patients with METH use disorder. Prior to this Phase 2 study, safety and pharmacokinetics of a single 3-g dose in healthy volunteers will be established. IXT-m200 will be administered via IV infusion over 30 min. This is necessary because it is a protein medication and would be metabolized to inactive components in the gastrointestinal tract if administered orally. The volume that must be given is too large to allow for intramuscular or subcutaneous administration based on the current formulation. This will result in a rate of 40 mg/kg/hr in a 75-kg person, which is significantly lower than doses given during a multiple-dose GLP toxicology study in which the slowest rate for the high dose was 1800 mg/kg/hr.

## **2. Trial Design and Methods**

### **2.1 Study Objectives**

#### **2.1.1 Primary Objectives**

- To evaluate the safety and tolerability of a single 3-g intravenous dose of IXT-m200 in healthy participants.

#### **2.1.2 Secondary Objectives**

- To characterize the pharmacokinetics of IXT-m200 following a single 3-g intravenous dose of IXT-m200 in healthy participants.

### **2.2 Study Overview**

Approximately 9 participants will be enrolled in the study in a single cohort. Participants will be randomized to 3 g IXT-m200 or placebo at a 7:2 ratio. Each will receive their dose as a 30-min IV infusion, then remain at the study site overnight to complete Day 1 and Day 2 assessments (e.g., ECG, laboratory assessments, blood draws, and vital signs). Following discharge on Day 2, participants will return to the clinic for follow-up PK and safety assessments on Day 8, then every 1-3 weeks thereafter until Day 127.

### **2.3 Sample Size Considerations**

Nine healthy adults will be randomized into the study. The sample size chosen for this study is not based on statistical considerations. The number of participants within each dose group was chosen based on historical experience with safety and pharmacokinetic trials and to match the study design used in the previous Phase 1 study with IXT-m200 which provided adequate safety and pharmacokinetic data. The sample size falls within the range of those used in other studies of this nature.

### **2.4 Selection and Withdrawal of Participants**

#### **2.4.1 Inclusion Criteria**

Participants must meet the following inclusion criteria:

1. Be at least 18 years of age at the time of study consent;
2. Be able and willing to read, comprehend, and give Authorization for Use/Disclosure of Health Information (HIPAA) and informed consent;
3. Be healthy, based on the pre-study medical evaluation (medical history and physical exam, vital signs, ECG, and clinical laboratory evaluations);
4. Be willing to comply with study instructions and dosing, agree to make all appointments, and complete the entire course of the study;
5. Be of nonchildbearing potential or agree to use protocol-specified method(s) of birth control throughout study participation;

6. Agree to adhere to Lifestyle Considerations throughout study duration (see protocol section 5.3).

## **2.4.2 Exclusion Criteria**

Participants meeting any of the following criteria will be excluded from the study:

1. Have a history of treatment with a monoclonal antibody in the past year;
2. Have a known contraindication or sensitivity to IXT-m200 based on known allergies to other mAbs, any inactive ingredient of IXT-m200, or any other products required for the study procedures;
3. Have a history of alcohol and/or drug use disorder, as determined by DSM-5 criteria;
4. Have a history of stimulant use, including methamphetamine and amphetamine;
5. Be currently taking certain other drugs and medications, including: “designer drugs” (e.g., 3,4-methylenedioxymETH (MDMA, Ecstasy, Adam, XTC) and its N-dimethyl metabolite methylenedioxymphetamine (MDA), anti-orexigenic drugs (including over-the-counter medications for weight loss), or be chronic users of phenethylamine compounds (e.g., phenylpropanolamine, ephedrine, pseudoephedrine, amphetamine, phentermine, phenmetrazine, methylphenidate, diethylpropion, and propylhexedrine);
6. Have a positive drug screen for any psychoactive substances (legal or nonlegal) on Day 1 prior to dosing;
7. Have a history of severe allergy (rash, hives, breathing difficulty, etc.) to any medications;
8. Have a history of allergic or environmental bronchial asthma within the past 3 years;
9. Have a clinically significant history of or current abnormality or disease of any organ system, including renal, hepatic, gastrointestinal, cardiovascular, pulmonary (including chronic asthma), endocrine (e.g., diabetes), central nervous (e.g., psychiatric conditions), or hematologic systems, or recent clinically significant surgery,
10. Have a history of seizure, epilepsy, severe head injury, multiple sclerosis, or other known neurological conditions,
11. Have a planned or scheduled surgical procedure during the study;
12. Have recently donated blood or plasma (within 30 days of study drug dose);
13. Have a current diagnosis of anorexia nervosa or bulimia disorder;
14. Be currently participating or has participated within the last 30 days prior to the start of this study in a drug, device, or other interventional research study;
15. Be pregnant or lactating;
16. In the Investigator’s or Sponsor’s (or designee) opinion, be inappropriate for the study.

## **2.5 Criteria for Individual Participant Discontinuation of Protocol Therapy**

The Investigator may discontinue a participant from study drug administration for the following reasons:

- the participant meets an exclusion criterion (either newly developed or not previously recognized) that precludes further study participation, such as an infusion reaction,
- any clinical AE, laboratory abnormality, or other medical condition or situation occurs such that continued participation in the study would not be in the best interest of the participant,
- significant non-compliance by the participant,
- if, in the Investigator's opinion, continuation with study drug administration would be detrimental to the participant's well-being,
- at the specific request of InterveXion (Sponsor) or the Investigator.

In all cases, the reason for withdrawal or discontinuation must be recorded in the CRF and in the participant's medical records. If the reason is not known, an attempt must be made to follow up with the participant to establish whether the reason was an AE, and, if so, this AE must be reported. Once the participant has been contacted and expresses their decision to withdraw from further participation in the study, the research staff will cease to try to make further contact.

## **2.6 Criteria for Individual Participation Discontinuation from the Trial**

Participants who withdraw consent for future study visits (following early termination assessments) will be considered 'withdrawn'. Participants are free to withdraw at any time upon request; they will be asked to complete early termination assessments as soon as possible. Participants that receive less than the complete single dose of study drug but agree to continue participation in other study procedures and assessments will be considered 'discontinued'. Participants are free to discontinue at any time during dosing upon request.

## **2.7 Handling of Participant Withdrawals or Discontinuation of Study Intervention**

Participants will be encouraged to complete study visits and assessments, even if they elect to discontinue study drug administration. In this case, all study activities will be completed per protocol with the exception of dose administration.

## **2.8 Replacement of Participants**

Participants who withdraw or are discontinued may be replaced at the Sponsor's discretion until there are 6 participants who have completed the protocol through Day 63.

## **2.9 IXT-m200 Dosing and Administration**

Participants will only be randomized and dosed with study drug if they have passed all screening requirements before or on Day 1. Participants will be randomized on Day 1 to receive 3 g IXT-m200 or placebo (7:2).

Each participant will receive 1 dose of assigned study drug on Day 1. Participants should lie supine or semi-reclined during dose administration. Each dose will be given with an infusion

pump over 30 minutes with a 50-mL saline flush dispensed after the dose to ensure the entire dose is flushed through the infusion set. The study drug infusion start/stop time, infusion rate, infusion volume, whether the infusion was completed, if it was stopped, or stopped and restarted will be recorded.

## 2.10 Schedule of Events

**Table 2-1 Schedule of Events**

Assessment a	Screening	Inpatient		Follow-up ( $\pm 1$ day)	Follow-up ( $\pm 3$ days)		ET
Study Week	$\leq -1$	1		2	3-17	18	NA
Study Day	-30 to -1	1 b	2	8	15, 22, 29, 36, 43, 64, 85, 106	127	NA
Informed consent	X						
Initial evaluations							
Eligibility criteria							
Demographics							
Medical history and medications							
Vital signs c							
Physical exam							
Psychiatric evaluation							
Urine pregnancy test							
Laboratory tests d	X	X	X	X	X (29 and 64 only)		X
Urine drug screen		X					
Wellness check							
Update medical history							
Update medications		X	X		X		X
Vital signs c							
Targeted physical exam							
ECG e		X					
Urine pregnancy test		X				X	X
Blood for cytokines f		X					
Blood for PK g		X	X	X	X	X	X
Blood for HACA h		X				X	X
Randomization		X					
Dose administration i		X					
AE monitoring				Continuous			X

Abbreviations: ECG – electrocardiogram; ET – early termination visit; HACA – human anti-chimeric antibodies; NA – not applicable; PK – pharmacokinetic

- a) Descriptions of assessments are in Section 8.1 of the Protocol.
- b) Study Day -1 is the day prior to the first dose. Study Day 1 is the day of the first dose.
- c) Vital sign measurements will be taken on Day 1 starting with a pre-dose measurement ( $\leq 30$  min prior), then 0.25, 0.5, 1, 2, and 4 hours ( $\pm 5$  min) after dosing starts, and as needed afterward until normalization. Measurements will be obtained once on each non-dosing day. Each test may be repeated once at each time point if the initial result is out of range.
- d) Laboratory tests require blood and urine sampling for hematology, serum chemistry, and urinalysis. Samples are to be taken at screening, pre-dose and 2-hr post-dose completion ( $\pm 10$  min) on Day 1, and once on Days 2, 8, 29, and 64.

- e) ECGs are to be done pre-dose (up to 2 hr prior) and 30-min post-dose completion ( $\pm 15$  min) on Day 1.
- f) Cytokine samples are to be taken pre-dose ( $\leq 60$  min prior) on Day 1. If a participant has an infusion reaction, cytokine sampling at 1- and 4-hours post-dose ( $\pm 10$  min) should be performed. If no infusion reaction is observed, pre-dose samples will not be analyzed.
- g) PK samples are to be taken pre-dose ( $\leq 30$  min prior), then 1, 4, and 8 hr ( $\pm 10$  min) and 24 hr ( $\pm 30$  min) after the start of the infusion on Day 1. All other PK samples are to be collected once each visit.
- h) HACA samples are to be taken pre-dose ( $\leq 60$  min prior) on Day 1 and once on Day 127.
- i) Doses will be given over 30 min by IV infusion

## 2.11 Study Endpoints

### 2.11.1 Primary Endpoints

The primary endpoint for the study is number of participants with treatment-related AEs assessed by physical examinations and vital sign, ECG, and clinical laboratory testing.

### 2.11.2 Secondary Endpoints

The secondary endpoint is the time course of IXT-m200 concentrations. This will be examined by determining the IXT-m200 serum pharmacokinetic (PK) parameters derived from the serial serum concentrations following single-dose IV administration, including  $C_{max}$ ,  $T_{max}$ ,  $K_{el}$  ( $\lambda_z$ ),  $AUC_{last}$ ,  $AUC_{inf}$ , MRT, CL, and Vd and other PK parameters as data permit.

## 3. Efficacy Assessments

Not Applicable.

## 4. Pharmacokinetic Assessments

Serum IXT-m200 PK parameters will be calculated from serum concentration data determined using a validated bioanalytical method. Pharmacokinetic parameters will be calculated using noncompartmental analysis methods suitable for intravenous infusion. Pharmacokinetic parameters that will be calculated if data permit are presented in **Table 4-1**.

**Table 4-1 Pharmacokinetic Parameters**

Parameter	Description	Method of Determination
$C_{max}$	Maximum serum concentration (observed)	Observed directly from data
$T_{max}$	Time to maximum serum concentration (observed)	Observed directly from data
$C_{last}$	Serum concentration at last measurable time point (observed)	Observed directly from data

$T_{last}$	Time to last measurable serum concentration (observed)	Observed directly from data
$AUC_{last}$	Area under the serum concentration-time curve from zero (start of infusion) to last quantifiable time point	$AUC = \sum \Delta t^* (C_1 + C_2)/2$
$AUC_{inf}$	Area under the serum concentration-time curve from zero (start of infusion) extrapolated to infinity	$AUC_{inf} = AUC_{last} + C_{last}/\lambda_z$
$K_{el}$ or $\lambda_z$	Elimination rate constant associated with the terminal elimination phase	$K_{el}$ is calculated by a linear regression of the log-linear concentration-time curve.
$t_{1/2}$	Terminal elimination half life	$t_{1/2} = \ln(2) / \lambda_z$
CL	Systemic clearance	$CL = \text{Dose}/AUC_{inf}$
$V_z$	Volume of distribution based on the terminal phase.	$V_z = \text{Dose}/[\lambda_z(AUC_{inf})]$
$V_{ss}$	An estimate of the volume of distribution at steady-state	$V_{ss} = MRT_{inf} * CL$
$MRT_{last}$	Mean residence time (MRT) from zero to last quantifiable time point	$AUMC_{last}/AUC_{last} - TI/2$ TI is the length of infusion
$MRT_{inf}$	Mean residence time (MRT) extrapolated to infinity	$AUMC_{inf}/AUC_{inf} - TI/2$ TI is the length of infusion

## 5. Safety Assessments

All safety analyses will be performed on the Safety population. Descriptive statistics will be used to summarize AEs, serious AEs, AEs causing withdrawal or discontinuation from the study, AEs judged by the Investigator as potentially related to study drug, changes in laboratory and vital signs, and immune response by measurement of anti-IXT-m200 antibody levels. AEs will be tabulated by Medical Dictionary for Regulatory Activities (MedDRA) system organ class (SOC) and preferred term.

Other safety observations and measurements will include vital signs, physical exam, pregnancy test, laboratory tests, and ECG. Descriptive statistics will be used to summarize continuous variables and change from baseline. Frequency and shift tables will be created for categorical variables.

## **6. Data Analysis and Statistical Considerations**

### **6.1 General Considerations**

Sample size was selected empirically without consideration of statistical power. As a result, no formal statistical hypothesis will be evaluated. Draft statistical summaries will be provided during the course of the study using dummy treatment code. The final report will be generated when all corresponding data are collected and database locked and treatment code released per Symbiance SOP. Statistical tables, data listings, and graphs will be prepared using SAS Version 9.4 or higher (SAS Institute, Cary, North Carolina, USA).

### **6.2 Analysis Populations**

**Pharmacokinetic Population:** All participants who receive active study drug and have at least one measured IXT-m200 concentration at a scheduled PK time point after start of dosing comprise the PK Population. If participants do not receive a complete dose or have incomplete data, a decision will be made on a case-by-case basis as to their inclusion in the analysis. This population will be used for all PK summaries.

### **6.3 Safety Population: All participants who receive exposure to study drug, including placebo comprise the Safety Population. This population will be used for all demographic and safety summaries. Safety Analyses**

Safety analyses will be presented by IXT-m200 and placebo groups and for all participants in the safety population.

Treatment-emergent adverse events (TEAEs) and serious TEAEs will be summarized by SOC and preferred term, and by severity (Grades 1, 2, 3, or 4) and relationship to treatment for IXT-m200 and placebo groups. The analysis of TEAEs by severity will count TEAEs by worst severity if an individual participant has a TEAE with more than one severity. The analysis of TEAEs by relationship to treatment will define treatment-related TEAEs as including all TEAEs assessed as definitely, probably, or possibly related to treatment, and non-treatment-related TEAEs as including all TEAEs assessed as unlikely and unrelated to treatment.

Vital signs, physical exam, pregnancy test, laboratory tests, and ECG will be tabulated. Descriptive statistics will be used to summarize continuous variables and change from baseline, which is defined as the most recent observation before dosing. Frequency and shift tables will be created for categorical variables.

### **6.4 Pharmacokinetic Analyses**

Pharmacokinetic parameters will be calculated using Phoenix WinNonlin Version 8.3 or higher (Certara USA, Princeton, New Jersey, USA).

#### **6.4.1 Serum Concentrations**

Serum concentrations of IXT-m200 will be listed with nominal sampling times for all participants in the PK Population.

Serum concentrations will be summarized using descriptive statistics for each treatment. Below the limit of quantitation (BLQ) concentrations will be treated as zero for the computation of descriptive statistics. Concentrations assigned a value of missing will be omitted from the calculation of descriptive statistics.

Mean and individual IXT-m200 serum concentration versus nominal time will be displayed in the figures (linear and semi-logarithmic scale) by dose and participant. Graphs may be generated in SAS or WinNonlin (or both) applications.

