7.3 LOST TO FOLLOW-UP

A participant will be considered lost to follow-up if he or she fails to return for the final scheduled visit, including an early term visit, and is unable to be contacted by the study site staff.

The following actions must be taken if a participant fails to return to the clinic for a required study visit:

- The site will attempt to contact the participant and reschedule the missed visit, counsel the participant on the importance of maintaining the assigned visit schedule, and ascertain if the participant wishes to and/or should continue in the study.
- Before a participant is deemed lost to follow-up, the Investigator or designee will make every effort to regain contact with the participant (where possible, 3 telephone calls and, if necessary, a certified letter to the participant's last known mailing address or local equivalent methods). These contact attempts should be documented in the participant's medical record or study file.
- Should the participant continue to be unreachable, he or she will be considered to have withdrawn from the study with a primary reason of lost to follow-up.

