#### **6.4.2 Pharmacokinetic Parameters**

Pharmacokinetic parameters will be derived from IXT-m200 serum concentrations using actual doses administered and actual sampling times of blood collection for each participant in the PK Population. Descriptive statistics will be summarized by dose. Descriptive statistics (mean, standard deviation (SD), coefficient of variation (CV%), geometric mean, geometric SD, geometric CV%) will be reported for all PK parameters, except for  $T_{max}$  where N, median, min, and max will be reported.

Predose samples that are BLQ or missing will be assigned a numerical value of zero for the calculation of area under the concentration-time curve (AUC). Any other BLQ concentrations will be assigned a value of zero if they precede quantifiable samples in the initial portion of the profile. A BLQ value that occurs between quantifiable data points, especially prior to  $C_{max}$ , will be evaluated to determine if an assigned concentration of zero makes sense, or if reanalysis or exclusion of the data is warranted. Following  $C_{max}$ , BLQ values embedded between 2 quantifiable data points will be treated as missing when calculating AUC. If BLQ values occur at the end of the collection interval (after the last quantifiable concentration), these will be treated as missing data. If consecutive BLQ concentrations are followed by quantifiable concentrations in the terminal portion of the concentration curve, these quantified values will be excluded from the PK analysis by assigning them a value of missing, unless otherwise warranted by the concentration-time profile.

The linear-log trapezoidal rule will be applied for the calculation of AUC parameters in the noncompartmental analysis model. Pharmacokinetic parameters presented in **Table 4-1** will be listed by participant and summarized. Graphical presentations of PK data may be added at the discretion of the PK scientist.

Pharmacokinetic parameters derived with  $K_{el}$  such as  $t_{1/2}$  and  $AUC_{inf}$ , will be listed but excluded from descriptive statistics if  $R^2_{adjusted} < 0.8$  in  $K_{el}$  estimation.

For determination of  $AUC_{inf}$ , if the percentage of extrapolated AUC is more than 20% of  $AUC_{inf}$  from  $t_{last}$  to infinity, then individual  $AUC_{inf}$  result and the PK parameters depending on  $AUC_{inf}$  (CL, Vz, and  $MRT_{inf}$ ) will be listed but flagged as not reliable calculations.  $AUC_{inf}$  and

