### 7.2 Drop-outs, Withdrawals, Replacement Policy

Participants who withdraw or are discontinued may be replaced at the Sponsor's discretion until there are 6 participants who have completed the protocol through Day 63. In case a discontinued participant is replaced, both the original and replacing participants will be included in the relevant listings and AE reporting.

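### Does the early-termination PK sample need a placement rule, given that SAP 6.4.1 displays concentrations by nominal time?

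*SAP*

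**What the plan says.** SAP 6.4.1 sets the time basis for the concentration displays. On the listing: "Serum concentrations of IXT-m200 will be listed with nominal sampling times for all participants in the PK Population". On the graphs: "Mean and individual IXT-m200 serum concentration versus nominal time will be displayed in the figures". Concentrations are also summarised by treatment, with no time basis named; the mean figure implies nominal time.

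SAP Table 2-1 has an ET column with blood for PK marked. Its study week and study day are NA, which the abbreviation line explains: "ET – early termination visit; HACA – human anti-chimeric antibodies; NA – not applicable". Footnote g fixes the Day 1 times and then adds "All other PK samples are to be collected once each visit". The collection windows are ±1 day at Day 8 and ±3 days from Day 15 to Day 127.

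The ET visit can fall on any day. SAP 2.6 says of participants who withdraw that "they will be asked to complete early termination assessments as soon as possible". For a missed visit, Protocol 7.3 says "The site will attempt to contact the participant and reschedule the missed visit". SAP 7.2 lets the sponsor replace participants "until there are 6 participants who have completed the protocol through Day 63".

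The PK parameters have a different time basis. SAP 6.4.2 derives them from "actual sampling times of blood collection for each participant" and from the doses actually given.

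**The concern.** A nominal-time display needs a nominal time for every point, and the schedule gives the ET sample none. The SAP text does not say whether to drop the sample, attach it to the nearest visit or attach it to the next planned one. It also has no rule for follow-up samples taken outside their windows.

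Two consequences seem possible. First, for someone who leaves early, the ET sample can set Clast and Tlast in the parameter table yet have no position on that person's concentration curve, so the two outputs would be hard to reconcile. Second, with about 7 active participants, one misplaced value shows in a visit mean, and the convention might be chosen with the data in hand. The time course is the secondary endpoint, and the replacement provision shows that early leavers were considered possible.

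**Working it through.** **Inputs.** Half-life about 18 days (SAP 1.2). Allocation 7:2 of about 9 participants (SAP 2.2), so 9 × 7/9 = 7 active. Visit days and windows from SAP Table 2-1. The plan states no figure on this point to reproduce. As a check on the half-life, SAP 1.2 also gives a volume of about 5 L and a clearance of about 200 mL/day: ln 2 × 5000/200 = 17.3 days, in line with 18.

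**Assumptions.** Mono-exponential decline after Day 8; all other participants equal at the visit in question. A half-life range of 14 to 22 days is my assumption around the stated value.

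**1. Days on which a sample falls outside every window.** These are Days 3–6 (4 days), 10–11 (2), and 47–60, 68–81, 89–102 and 110–123 (14 each): 4 + 2 + 4 × 14 = 62 of the 121 days from Day 3 to Day 123. From Day 47 onward it is 56 of 77 (73%). These are calendar counts, not probabilities; the documents give no drop-out rate.

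**2. Error in one value if it is relabelled.** A sample taken d days before the day it is labelled with is too high by the factor 2^(d/18); one taken d days after is too low by the inverse.

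- Nearest visit, up to 10 days early (Day 54 labelled Day 64): 2^(10/18) − 1 = +47.0%.
- Nearest visit, up to 10 days late (Day 53 labelled Day 43): 2^(−10/18) − 1 = −32.0%.
- Next planned visit, up to 17 days early (Day 47 labelled Day 64): 2^(17/18) − 1 = +92.4%.
- Inside a ±3-day window, for comparison: +12.2% or −10.9%.

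**3. Effect on a visit mean of 7.** Divide by 7.

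| Rule | 18 days | 14 days | 22 days |
|---|---|---|---|
| Nearest visit, upper end | +6.7% | +9.2% | +5.3% |
| Next visit, upper end | +13.2% | +18.9% | +10.1% |

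The lower end for the nearest visit at 18 days is −32.0/7 = −4.6%. Leaving the sample out moves nothing under these assumptions.

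**4. How far these are worst cases.** The −4.6% needs a participant with no sample of their own at the visit the ET result is attached to. Someone who attended Day 43 and then left already has a Day 43 value; averaging the two halves the effect to −32.0/2/7 = −2.3%. The +13.2% needs withdrawal on the first day after a window closes, together with a next-visit rule.

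**5. What the documents already settle.**

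- Listing: Protocol 9.4.4 lists collected data by timepoint, and ET is a named visit in the schedule, so the result can be listed under ET. SAP 6.4.2 also lists the Table 4-1 parameters by participant. These include Clast and Tlast, so if the ET sample is the last measurable one, its value and actual time are reported.
- Rescheduled visits: a Day 64 visit held late is still the Day 64 visit and keeps that nominal day. One held outside its window is a protocol deviation and is documented under Protocol 10.1.10.
- Individual curves: SAP 6.4.2 allows further PK graphs at the PK scientist's discretion, so an actual-time plot is available if needed.
- Parameters: AUC, clearance, half-life, volumes and residence times use actual times. Their change under any display convention is zero.

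**The case for a change.** The best argument for a change is that the gap is real and cheap to close. SAP 6.4.1 prescribes an axis on which a scheduled sample has no value. Calling it ET serves a listing, but it neither places a point on a nominal-time curve nor says whether the value enters a mean. The displays in 6.4.1 are the most direct picture of the secondary endpoint, and actual times must be collected for 6.4.2 anyway. The table and figure shells may hold a convention, but SAP section 1 puts them in a separate file that is not among the documents.

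The factual part stands: the SAP text is silent on the ET sample in figures and means. The argument for amending does not. Nothing turns on the choice: no hypothesis is tested (Protocol 9.1, SAP 6.1), and SAP 2.11.2 examines the time course through parameters the choice cannot touch. SAP 6.1 plans draft summaries under dummy treatment code during the study, so the convention can be settled before the treatment code is released. SAP section 8 requires consequential departures to be documented.

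A written rule could also do harm if drawn too broadly. Limiting means to samples inside their protocol windows would, on Day 1, remove an 8-hour sample drawn 11 minutes after its nominal time, because that window is ±10 minutes. At an 18-day half-life, 11 minutes changes the concentration by ln 2 × 11/(18 × 1440) = 0.03%, so a value would be lost from a mean of about 7 for no gain.

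**Conclusion.** No change to the plan follows. The SAP text leaves one display convention unwritten: how the ET sample, which has no nominal day, appears in the concentration figures and whether it enters the by-visit summaries. Listing it as ET with its actual time and keeping it out of the by-visit means is the obvious reading, and it moves no mean under the equal-participants assumption. Even the less sensible nearest-visit mapping moves a single visit mean by at most about −5% to +7%. Those limits rest on an 18-day half-life, mono-exponential decline, 7 otherwise equal active participants, and no other sample from that participant at the visit. The +13.2% for next-visit mapping is an extreme of timing. No PK parameter and no conclusion of this descriptive study depends on the choice.
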